Patients will be evaluated at 6, 12, 18, and 24 study months (\pm 2 months) for repeat swabs (1. one swab of both nares; 2. one swab of the throat; 3. one swab of the bilateral groin areas; 4. one swab of the axilla areas; and 5. one swab of the perirectal area). Patients will also complete questionnaires regarding recent antibiotic use, recent soft tissue infections, recent sexually transmitted diseases, hospitalizations, substance use, sexual activities, and activities previously associated with MRSA (refer to case report forms). Study coordinators will search the patient's medical records and the hospital computer database for medication use, medical conditions including MRSA or soft tissue infections, hospitalizations, sexually transmitted diseases, and HIV data including CD4 count, viral loads, and CDC staging.

Culture results regarding MRSA carriage are to be finalized within 3-4 days of collection. Patients found to have a positive culture for MRSA during the study period from the colonization swabs will be randomized in a 1:1 double-blinded fashion to mupirocin (Bactroban®) nasal ointment twice daily for seven days plus hexachlorophene (pHisoHex®) washes with showering once daily for seven days or to a placebo nasal ointment (white petroleum) and a placebo body soap with no antimicrobial activity for seven days. The patient will be randomized within 7 days of the receipt of the MRSA positive culture result. Women of childbearing age will have a urine pregnancy test to assure they are not pregnant before dispensing of these medications; women found to have a positive pregnancy will be terminated from the study.

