Patients experiencing an infection will be offered decolonization medications based on their most recent randomization assignment; those previously randomized will be maintained in their group, while those experiencing a soft tissue infection and having a positive colonization culture for the first time will be randomized to either mupirocin (Bactroban®) nasal ointment twice daily for seven days and hexachlorophene (pHisoHex®) washes with showering once daily for seven days or to a placebo nasal ointment (white petroleum) and a placebo soap with no antimicrobial activity for seven days. Patients with a positive soft tissue culture but no positive swabs from the nares, throat, groin, axilla, or perirectal areas, will not be randomized. If the primary clinician caring for a patient who experienced a MRSA infection desires to decolonize a patient regardless of the patient's randomization group, this is permitted, but must be documented and these participants will be removed from the "placebo group" for the analysis.

All cultures (from colonization sampling, wound and blood cultures) which are positive for MRSA or MSSA at the local medical treatment facilities laboratories will be preserved by freezing the isolates at -70 degrees C; these samples will be batched (isolates will be held at the primary facility and sent on a periodic basis) and sent overnight with dry ice to the NMCSD. This site will collect the specimens and send them to the laboratory at SAMMC which will perform testing on the isolates for confirmation of MRSA, antibiotic susceptibility testing (including mupirocin), and molecular analysis (to include multilocus sequence testing, PVL PCR, and other virulence factors). Some local laboratories (e.g. NMCSD) are also performing susceptibility testing on the isolates; this information will be collected if available. SAMMC will also repeat all susceptibility testing on all isolates at their facility. All samples sent to the laboratory at SAMMC will be labeled only with a PIN number of the patient. The staff at the SAMMC laboratory will not have access to personal identifiers and will have no way of linking their results to a patient name. Results

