will be reported to the study lead PI using this unique identifier, together with a SAMMC-assigned identifier. These data will be utilized to characterize the MRSA isolates colonizing and infecting HIV patients, understanding the relationship between colonizing and infection-related isolates, and to determine if HIV patients acquire new strains or remain colonized with the same strain over time.

The primary endpoint of the study is the effectiveness of decolonization procedures with application hexachlorophene (pHisoHex®) soaps and nasal mupirocin (Bactroban®) compared to placebo among patients found to be colonized with MRSA in the prevention of future colonization with MRSA. As a secondary part of the study's objectives, we will also examine the effectiveness of these decolonization procedures on infections with MRSA and on soft tissue infections.

The following assessments will be performed:

a. Clinical (Visits 1, 2, 3, 4, 5, unscheduled visits)

1. Informed Consent (visit 1 only)
2. Patient Questionnaires regarding medical history, medication use, and potential risk factors for MRSA
3. Demographics (visit 1 only)
4. Review of patients medical record by study coordinators
5. Study medication dispensing (unscheduled visits for positive MRSA colonization only)
6. Adverse event review (unscheduled visits in which patient receives a study medication only)
7. Medication adherence questionnaire (visit following decolonization therapy)

b. Laboratory Values (Visits 1, 2, 3, 4, 5, unscheduled visits)

1. Swabs for MRSA colonization of the nares, throat, groin, axilla, and perirectal areas (5 swabs)
2. Pregnancy test (visit 1; visits for MRSA colonization before decolonization medications are prescribed for women of childbearing age)
3. CD4 count and HIV viral load (MRSA or soft tissue infection visit only)
4. Blood cultures (two sets) at the physician's discretion (MRSA or soft tissue infection visit only)
5. Wound culture (MRSA or soft tissue infection visit only)

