6.4 Details of Laboratory Studies

Testing

Swabs for MRSA:	Patients will have their nares, throat, groin, axilla, and perirectal areas swabbed for MRSA colonization and these swabs will be sent to the microbiology laboratory at the clinical site for determination of the presence of MRSA or MSSA at each of these sites. The laboratory will provide culture results within 3-4 days of swab collection.
Wound and blood cultures:	Patients with an active skin or soft tissue infection will have a culture of the wound performed and sent to the microbiology laboratory of the clinical site for determination of the presence of MRSA or MSSA at each of these sites. Blood cultures may be ordered based on the discretion of the primary physician.
HIV studies:	CD4 count by flow cytometry and HIV viral load will be performed at each clinical site's lab.
Pregnancy test:	Women of childbearing age will have a pregnancy test at baseline to assure she meets inclusion/exclusion criteria. This test will be repeated if she is found to be colonized with MRSA before dispensing the decolonization medications; if she is found to have a positive pregnancy test, her study participation will be terminated.

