APPENDIX D: SCHEDULE OF EVENTS

Event	Visit 1	Visit 2	Visit 3	Visit 4	Visit 5	Positive MRSA Colonization visit	MRSA Colonization Follow-up visit	MRSA/Soft Tissue Infection Visit	Additional / Unscheduled Visit
Study Month (Window: months)	0	6 (±2)	12 (±2)	18 (±2)	24 (±2)				
Informed Consent	X								
Inclusion/Exclusion Criteria	X								
Urine Pregnancy Test for women of childbearing age	X					X [#]		X [#]	
Enrollment	X								
Questionnaires including Medical History, Medications and MRSA Risk Factors	X	X	X	X	X	X		X	
Demographics	X								
MRSA Swabs for Colonization	X	X	X	X	X		X	X	
Randomization*						X		***	
Dispense Drug*						X		***	
AE Review***							X		X
Drug Accountability							X		
CD4 count/HIV Viral Load**								X	
Wound Culture and possibly blood cultures****								X	
Study Completion					X				

[#]Pregnancy test will only be performed at the MRSA colonization and infection visits among women who found to be colonized with MRSA; those with a positive pregnancy test will not receive the study medications and will be terminated from the study.

*Randomization into the mupirocin (Bactroban®) and hexachlorophene (pHisoHex®) soaps or to the placebo arm will only occur if a patient has a positive colonization swab for MRSA. Patients will be randomized in a 1:1 double-blinded fashion into these groups. Patients with colonization, regardless of the group assigned, will have repeat swabs for MRSA performed monthly (+/- 7 days) for six consecutive months. For patients with repeat positive MRSA colonization swabs on the 6-month visits, will be re-randomized during each of these events.

**AE review will occur among patients given mupirocin (Bactroban®) and hexachlorophene (pHisoHex®) or the placebo ointment and soap. AE's will be assessed that are temporally associated with study medications.

***Patients who are also found to have positive colonization swabs in addition to an infection will be randomized to one of the two treatment groups if this patient was not already randomized and the same procedures for a positive colonization visit will be followed.

****Patients presenting with a soft tissue infection will have wound cultures obtained if possible. Blood cultures also may be obtained at the primary treating physician's discretion

XVIII. ATTACHMENTS

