patients will receive a medication information sheet recommending the avoidance of applying hexachlorophene (pHisoHex®) to areas of abraded skin. This medication is category C in pregnancy as large doses of hexachlorophene (pHisoHex®) given orally and intravaginally have proven embryotoxic and teratogenic in animal studies. Although there have been inadequate studies in humans, one retrospective review found an increased incidence of fetal malformations and minor deformities of children born to nurses washing their hands with hexachlorophene (pHisoHex®) 10-60 times daily [38, 44]. The risk of toxicity in this study is low since the soap will be only used once daily for seven days among patients found to carry MRSA. All females who become pregnant or plan on becoming pregnant will be excluded from this study.

The placebo ointment which is a white petroleum jelly may cause local reactions, such as burning, stinging, soreness and pruritis. The placebo body soap will not have an antibacterial properties; it may cause a local skin reaction such as dermatitis.

The risk of phlebotomy is excess bleeding, bruising, discomfort at the site of puncture, infection, and rarely “fainting” (vasovagal syncope). Phlebotomy is generally considered a minimal risk procedure. Blood draws will be obtained at the same time that laboratories ordered by the patient’s primary physician are drawn when possible. Patients will be closely monitored and have access to medical care 24 hours a day through the emergency room and Infectious Disease clinic.

18.C.7 Benefits

The benefit of the study includes the possibility of detecting MRSA colonization and clearing it to prevent infections from this organism. The risks of blood draws and topical mupirocin (Bactroban®) and hexachlorophen (pHisoHex®) soap or placebo ointment and soap are low. A study establishing guidelines on screening and decolonization of MRSA among HIV patients could lead to better healthcare and fewer soft tissue and MRSA infections in this population.

18.C.8 Informed Consent

A model informed consent form will be provided to each investigator. If the model informed consent is modified, a copy of the modified form must be provided to the Sponsor by the investigator for approval prior to submission to the IRB or EC. The final informed consent form must be approved by the IRB or EC.

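### Section 6.3 re-offers study product after an infection with no stated swab condition, but repeat pregnancy testing covers only colonized women: an inconsistency with a small, conditional safety gap

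*Combined protocol and SAP*

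**What the plan says.** All references are to the combined protocol and SAP.

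**Who gets another course.** The infection paragraph of Section 6.3 states: "Patients experiencing an infection will be offered decolonization medications based on their most recent randomization assignment". Those already randomized stay in their group. A positive colonization culture is named as a condition only for patients being randomized for the first time. A later sentence bars randomization of patients whose wound culture is positive but whose swabs are all negative. It does not mention patients who already hold an assignment.

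**Where product is dispensed.** Item a.5 of the Section 6.3 assessment list is narrower: "Study medication dispensing (unscheduled visits for positive MRSA colonization only". In Appendix D the drug-dispensing row has only a footnote marker at the infection visit. That footnote covers swab-positive patients who have not yet been randomized.

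**When the pregnancy test is repeated.** Item b.2 of the same list reads: "Pregnancy test (visit 1; visits for MRSA colonization before decolonization medications are prescribed for women of childbearing age". Section 6.4 says: "This test will be repeated if she is found to be colonized with MRSA before dispensing the decolonization medications". The Appendix D footnote is the most restrictive: "Pregnancy test will only be performed at the MRSA colonization and infection visits among women who found to be colonized with MRSA". The Section 6.3 paragraph on positive cultures says: "Women of childbearing age will have a urine pregnancy test to assure they are not pregnant before dispensing of these medications".

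**Risk.** Section 18.C.6 says of hexachlorophene: "This medication is category C in pregnancy". It adds: "The risk of toxicity in this study is low since the soap will be only used once daily for seven days", and the same sentence goes on to limit that use to patients found to carry MRSA. The opening of 18.C.6 likewise describes the products as given to colonized patients randomized to treatment.

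**The concern.** The re-offer and the pregnancy test have different triggers. The re-offer is triggered by an infection plus an existing assignment. The test is triggered by a finding of colonization. A patient can meet the first condition and not the second. If she is a woman of childbearing age whose latest assignment is active, the infection paragraph gives her hexachlorophene again, and no test is scheduled before that course. The plan tests before the other courses it describes, so this would be the one course without its own safeguard. An earlier negative test, at baseline or at a previous randomization, cannot exclude a pregnancy that began months later in a two-year study.

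Sites would also have to decide for themselves whether the infection paragraph or item a.5 governs, and they could decide differently.

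**Working it through.** The plan gives no figure on this point, so there is none to reproduce. The check has two parts.

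**1. One patient followed through the text.** Take a woman of childbearing age, previously randomized with latest arm active, who has a soft tissue infection and five negative swabs.

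- Section 6.3, infection paragraph: she is offered active product again.
- Section 6.3 item a.5: no dispensing, because this is not a positive-colonization visit.
- Appendix D, dispensing footnote: silent, because she is already randomized and not swab-positive.
- Section 6.3 item b.2, Section 6.4 and the Appendix D test footnote: no repeat test, because she was not found colonized.
- Section 6.3, positive-culture paragraph: a test before dispensing, but in a paragraph about culture-positive patients.

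The path closes if item a.5 overrides the infection paragraph, or if the positive-culture sentence is read as covering every dispensing despite the restriction in Appendix D. The text states neither.

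**2. How many women.** Inputs:

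- Active arm: 25 of 50 randomizations (Section VII goal of at least 50, allocated 1:1).
- Swab-negative share in the active arm: 1 - 0.39 = 0.61 to 1 - 0.07 = 0.93 (Section VII colonization rates after treatment).
- Infected per six months: 2% (40 per 1000 person-years, Section IV, × 0.5 year), 5% or 10% (treated-group planning rates, Section VII).
- Share of women: 5-20%. The documents do not give this, so it is an assumption.
- Carriage is taken as independent of infection, and every offer as accepted.

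Women = 25 × infected × swab-negative × share of women.

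| Infected | Infected patients | Swab-negative | Women (5% to 20%) |
|---|---|---|---|
| 2% | 0.5 | 0.305-0.465 | 0.305 × 0.05 = 0.015 to 0.465 × 0.20 = 0.093 |
| 5% | 1.25 | 0.76-1.16 | 0.038 to 0.233 |
| 10% | 2.5 | 1.53-2.33 | 0.076 to 0.465 |

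With the 38 per arm of Section 5.2, multiply by 38/25 = 1.52. The range becomes 0.023 to 0.707 per 76 randomizations.

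**Which way the inputs lean.** The count includes all women, although only those of childbearing age are tested. It would be lower if infected patients are colonized more often. Section VII warns that its infection rates may be too high for this population, but also that they were observed over 8-10 weeks. The 2% row counts MRSA infections only.

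**Extra tests.** With staff blinded, both arms are tested. The placebo swab-negative share is 1 - 0.85 = 0.15.

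- Low: (25 × 0.02 × 0.61 + 25 × 0.02 × 0.15) × 0.05 = 0.38 × 0.05 = 0.02.
- High (10% v 38% infected): (25 × 0.10 × 0.93 + 25 × 0.38 × 0.15) × 0.20 = 3.75 × 0.20 = 0.75.

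**The case against.** The best defence is that the infection paragraph is one loosely worded clause and everything else is consistent. It contrasts previously randomized patients with those whose colonization culture is positive for the first time, which suggests that the former are positive again. Every infected patient is re-swabbed, and the products are called decolonization medications. Item a.5, the Appendix D dispensing row and its footnote, and both statements in Section 18.C.6 assume carriers only. On that reading the triggers for dispensing and testing coincide and there is no gap. The exposure would in any case be tiny. Section 5.4 excludes pregnant women and those intending pregnancy, a baseline test is done, and Section 6.10 ends participation on pregnancy.

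Much of this stands. The weight of the text favours carriers only, and the low-risk statement in 18.C.6 has to be read with its limit to carriers. What does not follow is that the gap is closed. No sentence excludes an already-randomized, swab-negative patient from the re-offer, none says which provision governs, and none of the partial safeguards is a test at the infection visit.

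A reader might infer that the plan directs untested use of hexachlorophene, or that such use is bound to happen. The documents do not support that. Item a.5 forbids the dispensing that the infection paragraph appears to allow, so an untested course arises only where a site follows the latter.

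**Conclusion.** The point holds as an internal inconsistency with a conditional safety gap, at the lowest level of importance. If the infection paragraph is followed literally, about 0.015 to 0.47 women per 50 randomizations per six months could be offered hexachlorophene without a test before that course. At the 38 per arm of Section 5.2 the upper figure is 0.71 per 76 randomizations.

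These figures depend on the assumed share of women, on independence of carriage and infection, and on full acceptance of the offer. With no reduction for age or refusal, they are best read as a ceiling under those assumptions. They are not pregnancies, which would be far fewer given the exclusions, the baseline test and the termination rule.

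The as-randomized primary comparison is not affected, because the re-offer keeps the patient in her assigned arm. Sample size and error rates are not involved.

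**What to change.** **1. Test before every dispensing.** Require a negative urine pregnancy test for women of childbearing age before any study product is dispensed, whatever the swab result. Put this in four places: the infection paragraph of Section 6.3, item b.2 of its assessment list, Section 6.4, and the Appendix D pregnancy-test footnote. This closes the gap under either reading. It also protects a woman given product on the day of an infection visit, before the 3-4 day culture result is known. The cost is four short edits and at most about 0.02 to 0.75 extra urine tests per 50 randomizations per six months.

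**2. Settle who is re-dispensed product.** Preferably, add one sentence to the infection paragraph: an already-randomized patient receives product again only if the swabs at the infection visit are MRSA-positive. This agrees with item a.5, Appendix D and Section 18.C.6. The cost is that product waits 3-4 days for the culture, and about 0.3 to 2.3 infected, swab-negative patients per 25 in the active arm are not re-treated.

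If the sponsor does intend to re-treat swab-negative patients, item a.5, the Appendix D dispensing row and footnote, and both carrier statements in Section 18.C.6 must all change. Item 1 is then essential.

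Decolonization chosen by the treating clinician outside the assignment remains clinical care and is not covered.

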3.1 Primary Objectives

To evaluate the effectiveness of decolonization procedures with application of hexachlorophene (pHisoHex®) soaps and nasal mupirocin (Bactroban®) compared to a placebo soap and nasal ointment which have no antibacterial activity among patients found to be colonized with MRSA in the prevention of future colonization with MRSA. As a secondary part of this objective, we will examine the impact of decolonization procedures on both infections with MRSA and soft tissue infections. In addition, as a sub-analysis to the primary objective, we will evaluate the impact of decolonization among unique randomizations (persons with first time MRSA colonization and randomization during the study).

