Patients who are colonized with MRSA and who reside locally to the medical treatment facility and are able to return to the clinic will have repeat swabs (five swabs from sites listed above) every month (+/- 7 days). A month will be specifically defined as 28 days. Those who have repeat positive colonization swabs during this initial 6 month follow-up period will be observed. This data will assess the efficacy of decolonization procedures on MRSA carriage rates. Patients who are not local to the clinic will not have these repeat swabs performed, but rather will be seen at the next scheduled 6 month study visit. Adherence to the study medications will be assessed at the next scheduled study visit by a patient questionnaire (refer to case report forms). Each time a patient has a positive isolate for MRSA or MSSA, this will be frozen and saved for molecular analysis to determine the most common molecular types colonizing HIV patients and to determine if patients acquire new strains or remain colonized with the same strain over time.

All study patients (both those initially found to be colonized with MRSA and those with negative colonization swabs) will be re-evaluated in six month intervals ($+/- 2$ months) until the end of the study. Patients found to be positive at these subsequent 6 month intervals, will be randomized again, treated and followed as described above. During the last study visit (at the 2-year time period), patients will have swabs, but not undergo randomization. Hence, every 6 months, patients positive during that visit for MRSA colonization will be re-randomized in a 1:1 double-blinded fashion to mupirocin (Bactroban®) nasal ointment twice daily for seven days plus hexachlorophene (pHisoHex®) washes with showering once daily for seven days or to a placebo nasal ointment (white petroleum) and a placebo body soap with no antimicrobial activity for seven days. Repeat randomization will occur every 6 months for those carrying MRSA. For example, some patients initially randomized to receive Bactroban® and pHisoHex®, may later be randomized to the placebo arm, and vice versa.

Begin at the top of diagram again every 6 months ($+/- 2$ months). If patient is found to be positive on swabs, they are re-randomized to one of the two treatment groups for every 6-month positive swab.

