Patients will be asked to report to their enrolling HIV clinic for any soft tissue infections or any infection thought to be secondary to MRSA; if able, cultures of the wound site will be obtained. Blood cultures will be obtained at the primary provider's discretion depending on the presence of fevers, toxemia, and the extent of soft tissue involvement. Patients will also have repeated screening for colonization including nares, throat, groin, axilla, and perirectal swabs (5 total swabs) at this time. CD4 counts and an HIV viral load will be obtained at the time of the soft tissue infection or with any MRSA infection for patients presenting to the enrolling site. Patients with positive wound culture and/or blood cultures for MRSA will be classified as a "MRSA infection." Those with a soft tissue infection without positive cultures from these sites will be classified as a "Soft Tissue Infection NOS." The patient will be treated with intravenous or oral antibiotics and/or surgical procedures at the discretion of the medical provider that the patient presents to for evaluation. Patients who have an infection while located remotely from the HIV clinic will be given a contact information card and will be asked to call the site PI or study coordinator at their enrolling site to notify them of the infection. The site PI or study coordinator will try to arrange for the aforementioned tests to be performed at the local medical clinic; CD4 counts and HIV viral loads will not be performed for patients presenting remotely to the enrolling site. In addition, coordinators will gather information on the tests and treatments performed. Patient questionnaires will be completed for patients experiencing a soft tissue infection or MRSA infection (refer to case report forms).

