6.10 Termination

A subject's participation will be terminated if one of the following occurs:

- a. Subject voluntarily withdraws
- b. Subject fails to comply with study procedures
- c. Decision in the best interest of the patient
- d. Patient is no longer eligible for care at the military HIV clinics
- e. Patient becomes pregnant or decides to become pregnant during the two-year study period

- f. The patient begins employment as a healthcare worker with direct patient contact

A subject who develops a rash or significant adverse event due to study medication will be discontinued from treatment but will be encouraged to continue to undergo follow up including study visits for completing questionnaires and swabs for MRSA colonization every 6 months (+/- 2 months) until study completion; the patient will not be randomized to one of the treatment arms if he/she is found to be positive again for MRSA colonization. The subject may be withdrawn from the study if it is felt by the clinical investigators that the subject is at an undue risk from further participation.

The subject will require a termination visit if withdrawn from the study. If a subject's participation in this study is terminated, they will be offered medical standard of care and a medical evaluation, to include clinical laboratory studies as needed. The investigator will complete the Completion/Discontinuation CRF.

VII. STATISTICAL ANALYSES

There are four primary questions to be answered to address this study's primary objective. These, and an analysis designed to answer the question, follow.

- (1) What is the hexachlorophene/mupirocin treatment effect to clear MRSA colonization compared to placebo? We will also examine if these decolonization procedures are effective at reducing MRSA infections and skin/soft tissue infections compared to placebo. We propose to pool the data at 6, 12, 18, and 24 months as if they were independent and conduct a chi-square or Fisher's exact test of contingency. These analyses will be conducted for colonization and infection separately. The proposed pooling of this study design assumes that there is no persistent or repeated-treatment effect and that there is no patient-to-patient difference in susceptibility. These effects will be investigated in the following questions.

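### Clinician-decolonized patients are removed from the placebo group only, after an outcome event, and removal is undefined; most readings lose placebo infections from the secondary infection comparison

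*Combined protocol and SAP*

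**What the plan says.** Section 6.3 of the combined protocol and SAP covers the patient whose clinician, after an MRSA infection, "desires to decolonize a patient regardless of the patient's randomization group". This is allowed, but it "must be documented and these participants will be removed from the 'placebo group' for the analysis". No rule is given for active-arm patients who are decolonized in the same way.

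Three other statements in Section 6.3 bear on this:

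- After an infection the assigned medication is offered again: "those previously randomized will be maintained in their group".
- An infection can come before the first randomization: "those experiencing a soft tissue infection and having a positive colonization culture for the first time will be randomized".
- The arm can change at each six-month re-randomization; a patient first given active treatment "may later be randomized to the placebo arm, and vice versa".

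Infection is an outcome of the trial. Section 3.1 says: "As a secondary part of this objective, we will examine the impact of decolonization procedures on both infections with MRSA and soft tissue infections". Section VII, question (1), repeats it: "We will also examine if these decolonization procedures are effective at reducing MRSA infections and skin/soft tissue infections compared to placebo". That comparison is a chi-square or Fisher test on data pooled over the six-month visits. Section VII names no as-randomized or per-protocol set and does not return to the removal rule.

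**The concern.** The clause reads like a contamination rule: a placebo patient who receives open decolonization is no longer an untreated control. But its trigger is an MRSA infection, which is one of the events being compared. Decolonization given after an infection cannot have caused that infection, so contamination is no reason to discard it.

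If the infected placebo patient leaves the analysis while an active-arm patient with the same history stays, events disappear from one arm only and active treatment looks worse than it is. Because removal is undefined, the analyst could also choose among several readings after seeing the data.

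**Working it through.** **Readings of removal**

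| Reading | Triggering post-randomization placebo infection |
|---|---|
| (a) patient dropped from the analysis | lost |
| (b) patient dropped for that six-month interval | lost |
| (c) patient moved to the active group | lost from placebo, added to active |
| (d) later results censored, infection counted first | kept |

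Three of the four lose the event. An infection that led to a first randomization is baseline, so removing that patient loses no event under any reading.

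**Plan's own figure first.** Section VII gives 860 participants for infection rates of 38% v 10%, power 0.80, alpha 0.05. The uncorrected two-sided formula is n = [1.96·√(2·0.24·0.76) + 0.842·√(0.38·0.62 + 0.10·0.90)]² / 0.28² = 35.3. With continuity correction, (35.3/4)·[1 + √(1 + 4/(35.3·0.28))]² = 42.2, so 43 per arm. Then 2 × 43 / 0.10 colonized = 860, as stated.

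**Inputs for the removal rule**

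- n = 25 per arm, from the 50–55 randomizations expected in Section VII (Section 5.2 implies about 38 per arm).
- p = placebo infection rate.
- s = share of infections that are MRSA: 1 for the MRSA outcome; 0.5 assumed for soft tissue infection, with 1 as the upper case for colonization.
- q = share of placebo patients with MRSA infection who are removed. Not in the documents; assumed 25% or 50%.

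The removed fraction is r = p·s·q, and the analysed placebo rate is (p − r)/(1 − r). Each removal is counted as a lost post-randomization event, so r is an upper bound where some infections led to a first randomization. The model covers one period, without re-randomization. Reading (b), narrower than (a), was not computed separately.

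**At the plan's HIV rates.** Two-year risk = 1 − exp(−2 × rate).

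| Rate per 1000 person-years | Two-year risk | Infections per 25 | Lost at q = 50% | Analysed placebo rate, dropped |
|---|---|---|---|---|
| 13 | 2.6% | 0.64 | 0.32 | 1.3% |
| 40 | 7.7% | 1.92 | 0.96 | 4.0% |

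For a single six-month interval the risks are 1 − exp(−0.5 × rate) = 0.65% and 2.0%, or about 0.16 and 0.5 infections per 25.

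**False finding of harm.** This is a two-sided Fisher test at 0.05 by full enumeration, with equal true rates, s = 1 and 25 per arm. Entries are the probability of a significant result with the placebo rate lower.

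| True rate, both arms | None removed | Dropped, q = 25% | Dropped, q = 50% | Moved, q = 25% | Moved, q = 50% |
|---|---|---|---|---|---|
| 4% | 0.02% | 0.02% | 0.02% | 0.07% | 0.2% |
| 8% | 0.2% | 0.4% | 0.5% | 1.0% | 3.1% |
| 10% | 0.4% | 0.8% | 1.3% | 1.8% | 5.8% |
| 30% | 1.1% | 4.0% | 11% | 8.6% | 29% |

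**Power at the plan's 38% v 10%, s = 0.5, 25 per arm.** With none removed, Fisher power is 53%. Dropping gives 49% (q = 25%) or 39% (q = 50%); moving gives 34% or 16%. With 38 per arm and q = 50%, power falls from 78% to 57% (dropped) or 24% (moved). The 38% is a soft tissue infection rate in soldiers, which Section VII says may exceed the rate in HIV patients.

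**Primary colonization endpoint.** Take 85% of placebo patients still colonized, all removed patients carriers, and q = 50%. The analysed rate is (0.85 − r)/(1 − r):

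- r = 0.38·0.5·0.5 = 0.095 gives 83.4%.
- r = 0.38·1·0.5 = 0.19 gives 81.5%.
- r = 0.08·1·0.5 = 0.04 gives 84.4%.

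**The case against.** The strongest reply is that the effect is negligible where it is most relevant. At the plan's HIV rates fewer than one placebo event is expected to be lost, even over two years at q = 50%, and the false-harm probability barely moves if patients are dropped. Blinding and the repeat offer of assigned medication may keep q low. The documents give no rate for HIV-positive carriers, and nothing in them supports 30% for this population. This stands: the higher rows show how the rule behaves, and are not forecasts.

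It is also fair that moving patients to the active group is a strained reading. The text says where they are taken from, not where they go, so the moved figures are an extreme case. Full removal is the most natural reading.

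The one-sidedness has a rationale too: an active-arm patient decolonized again has not crossed over, whereas a placebo patient has. That explains the intent, but it does not justify discarding an infection that came before the crossover.

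Finally, the outcome is secondary, and the bias has a sign only in expectation; a given dataset may show no change. Both points limit the severity. Neither makes the rule sound.

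**Conclusion.** The concern holds. Followed on its most natural reading, the clause deletes placebo patients because they had an outcome event, and the plan contains nothing that defines removal or overrides the clause with an as-randomized analysis. Under readings (a) to (c) the infection comparison is biased, in expectation, against active treatment; under (d) the triggering event is kept.

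Confidence in the defect is high and confidence in its size is low, because q and the infection rate in HIV-positive carriers are unknown. At the plan's HIV rates the practical effect may be small. It grows if infections are common or patients are moved between groups. The effect on the primary colonization endpoint is small. This should be fixed, mainly because the sign of the bias is known and the repair is cheap.

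**What to change.** **Minimum repair.** Define removal in Section 6.3, and state that a triggering infection occurring after randomization stays counted in the assigned arm.

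**Full repair.** Replace the removal clause, and add to Section VII, wording to this effect:

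- All randomized patients are analysed in the arm of their current randomization, for both colonization and infection.
- An MRSA infection after that randomization is an event in that arm; an infection that led to a first randomization is baseline.
- Clinician-directed decolonization is documented in both arms. A sensitivity analysis sets aside results after it until the next randomization, in both arms alike. For the chi-square or Fisher test, say explicitly that only results after the decolonization are excluded and the earlier infection remains counted.

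**Cost.** A few sentences and one sensitivity analysis; documentation of these decolonizations is already required. The price is a slight dilution of the colonization contrast, because placebo patients who received open decolonization stay in their arm. The clinician's freedom to treat does not change.
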